### **Costs and Compensation**

There are no costs to participate. No compensation will be provided to participants.

### **Subject Withdrawal and Study Completion**

Subject compliance will be monitored throughout the trial by study staff. If any contraindications to the study are identified, participants may be withdrawn by the investigators. Participants can be withdrawn at any point if the investigators feel it is in the participant's best interest or in the interest of study integrity. No information will be collected from withdrawn participants unless it is related to a continuing AE or SAE.

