## **5.3 Clinical Assessments**

**5.3.1 Primary Response Assessments:** The primary outcome measure is change in depressive symptoms assessed by the Hamilton Rating Scale for Depression (HRSD-24), which is the most widely used method of evaluating the effectiveness of treatments to relieve depression. HRSD-24 will be administered as part of a clinical interview by blinded investigators prior to beginning the treatments, then repeated before treatment #6 and at the end of treatments.

**5.3.2 Secondary Response Assessments to be acquired before each treatment:** Also as standard of care for patients receiving ECT, the participant will fill out the Quick Inventory of Depressive Symptomatology (QIDS-SR) which is a patient self-report measure of depressive symptoms prior to each treatment session. QIDS scores will also be used as a safety measure. If 2 consecutive QIDS scores indicate worsening of depressive symptoms, below pre-treatment values, the study participant will meet with one of the study Psychiatrists to discuss treatment alternatives. The Montreal Cognitive Assessment (MoCA), Generalized Anxiety Disorder scale (GAD-7), and Work and Social Adjustment Scale (WSAS) will be administered prior to beginning the treatments, then repeated before treatment #6, and 48-72 hours post treatment #10.

**5.3.3 Follow-up Assessments to be acquired monthly for up to 6-months post treatment period:** Follow-up assessments will include QIDS-SR, WSAS, and an opened ended question about the participant's experience during the study. Follow-up assessments will be administered over the phone or by email with a link to an electronic survey housed on REDCap (a secure online database). A voicemail may be left (with prior permission) regarding the follow-up assessments.

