### **6.3 Safety and Efficacy Monitoring**

All serious adverse events will be reported within 5 days to the Data and Safety Monitoring Board (DSMB) and IRB by the Principal Investigator or study coordinators. These would include life-threatening cardiac arrhythmias, respiratory arrest, myocardial infarction, stroke, and death. Moderate adverse events including worsening of depressive symptoms will be reported to the DSMB. An interim data analysis will be performed at the midpoint of this pilot investigation, after data is obtained from 5 participants in each of the treatment conditions. The study will be terminated if significantly greater negative outcomes are associated with either isoflurane treatment or propofol treatment.

Prior to each treatment, participants will fill out the QIDS-SR. HRSD-24 will be obtained at baseline, before treatment 6, and after treatment 10. All participants will be assessed before the 6th treatment. If participants in Low ISO/BS- or propofol treatment groups show clinical deterioration (defined by 2 consecutive QIDS scores below baseline OR a decrease in HRSD-24 before the 6th treatment), they will be offered treatment at the 80% burst suppression level (High ISO/BS+) as it has proven effective in reducing depression or ECT as the standard of care treatment. Participants in High ISO/BS+ treatment who show clinical deterioration, as defined above, will be offered ECT. All serious adverse events will be reported within 5 days to the DSMB by the Principal Investigator or study coordinators. The DSMB will also be notified within 10 business days if a study participant is showing signs of clinical deterioration (defined as 2 consecutive QIDS scores below baseline OR HRSD-24 below baseline). Progress reports will be submitted every 6 months. If a participant has a serious reaction to anesthesia, they will be withdrawn from the study.

As exploratory biomarkers, we will evaluate whether quantitative cortical EEG changes early in treatment (obtained from dual lead BIS data in each treatment session) are associated with subsequent remission in depressive symptoms.

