### **Risks of Worsening Depression**

During the psychiatric and HSRD-24 interviews, participants will be asked to answer questions about their symptoms that may be upsetting. The interviews will be conducted by experienced clinicians in Psychiatry who have expertise in managing emotional situations. If participants require additional support, they will be referred to their clinical provider or the UNI CrisisLine at [contact].

The study physicians will be monitoring participants' depressive symptoms at frequent intervals, and if symptoms get worse, we will discuss other treatment options available outside of the study. Treatments available after leaving the study may include ECT or medications.

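### Withdrawn participants have no observed final HRSD-24, because the plan stops data collection at withdrawal and does not separate stopping treatment from leaving the study

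*Combined protocol and SAP*

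**What the plan says.** The rule on data collection is in Subject Withdrawal and Study Completion (section 4.5): "No information will be collected from withdrawn participants unless it is related to a continuing AE or SAE". The same paragraph makes withdrawal broad: "Participants can be withdrawn at any point if the investigators feel it is in the participant's best interest or in the interest of study integrity".

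Section 6.3 adds a mandatory trigger: "If a participant has a serious reaction to anesthesia, they will be withdrawn from the study". In section 9.1, the paragraph on worsening depression says that other options will be discussed and continues: "Treatments available after leaving the study may include ECT or medications". Section 6.3 offers participants who deteriorate on low-dose isoflurane or propofol either high-dose isoflurane or ECT, and offers ECT to those on high-dose isoflurane. It does not say whether they then count as withdrawn or are still rated at treatment end.

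The timing of the last primary measurement is given in two ways. Section 6.3 says "HRSD-24 will be obtained at baseline, before treatment 6, and after treatment 10". Section 5.3.1, which names HRSD-24 change as the primary outcome, says the scale is given before treatment and "then repeated before treatment #6 and at the end of treatments". The Schedule of Activities shows it in a Post Tx column. Section 5.3.2 sets the companion scales (MoCA, GAD-7, WSAS) 48 to 72 hours after treatment 10.

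Section 7 excludes participants who lack needed data. Section 7.1 analyses response at treatment end (yes or no) by logistic regression.

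**The concern.** The withdrawal sentence governs data collection. Read with section 7, it means that a participant withdrawn before treatment end has no observed final HRSD-24 and is then left out of the Aim 1 comparison. Changing the analysis population alone would not repair this, because the scores would not have been taken.

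Withdrawal can plausibly depend on tolerance or on outcome: a serious reaction forces it, investigators may decide it, and worsening depression leads to a discussion of treatment elsewhere. A comparison restricted to those who remain is then no longer protected by randomization, whichever way the selection runs. With at most 15 per arm, a few such losses matter.

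Two other records are affected. The monthly QIDS and WSAS follow-up stops for these participants. So does the recording of new non-serious adverse events, although section 6.3 treats worsening of depressive symptoms as a moderate adverse event to be reported to the DSMB.

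**Working it through.** **Step 1. What exists for a withdrawn participant (sections 4.5, 5.3, 6.3, 7).**

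| Withdrawn | HRSD-24 on record | QIDS on record | Aim 1 analysis |
|---|---|---|---|
| Before the rating that precedes treatment 6 | Baseline only | Each session attended | Excluded |
| After that rating, before treatment end | Baseline and mid-course | Each session attended | Excluded |
| Not withdrawn, 10 treatments | Baseline, mid-course, final | All sessions | Included |

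A participant who stops before treatment 10 without being withdrawn fits no row. Under section 5.3.1 a final rating could be taken when that person's treatments end. Under section 6.3 the trigger, treatment 10, never occurs. The two sections have to be reconciled.

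**Step 2. Is there a stated figure to reproduce?** No. Section 4.5 gives up to 15 per arm by reference to an earlier study in which 8 participants were treated, with no dropout rate and no allowance for loss. All loss figures below are assumptions.

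**Step 3. Best- and worst-case bounds.** Let m of 15 be lost in each arm, and let r be the observed responders among the other 15 − m.

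- The rate for everyone randomized to that arm lies between r/15 and (r + m)/15, a width of m/15.
- The High minus Low difference lies between (r_H − r_L − m)/15 and (r_H − r_L + m)/15, a width of 2m/15.

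| m lost per arm (assumed) | Width per arm | Width on the difference |
|---|---|---|
| 1 | 1/15 = 7 points | 2/15 = 13 points |
| 3 | 3/15 = 20 points | 6/15 = 40 points |
| 5 | 5/15 = 33 points | 10/15 = 67 points |

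**Step 4. A worked table.** Assume 3 of 15 lost per arm. Take 9 of 12 responders observed on high dose (75%, the response rate that section 3 gives for the earlier study) and 4 of 12 on low dose (assumed). P-values are from an unadjusted two-sided Fisher test, used for simplicity in place of the planned regression with covariates.

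| Handling of the 6 lost | High | Low | Difference | p |
|---|---|---|---|---|
| Excluded, as planned | 9/12 | 4/12 | 42 points | 0.10 |
| Counted as non-responders | 9/15 | 4/15 | 33 points | 0.14 |
| Best case for high dose | 12/15 | 4/15 | 53 points | 0.009 |
| Worst case for high dose | 9/15 | 7/15 | 13 points | 0.72 |

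The last two rows differ by 53 − 13 = 40 points, as Step 3 gives for m = 3.

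**Step 5. Effect of continued assessment.** If u of the m per arm still cannot be rated, through refusal or loss of contact, the width becomes 2u/15. With m = 3 and u = 1 it falls from 40 to 13 points.

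**The case against.** Several stronger readings are tempting, and the documents do not support them.

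- **Everyone who stops early lacks a primary outcome.** The rule covers participants who are withdrawn. The plan never says that stopping treatment is the same as withdrawal, and the wording of section 5.3.1 allows a final rating after fewer than 10 treatments. What stands is an unresolved ambiguity for those who stop, and a definite loss for those withdrawn.
- **No analysis can recover the result.** The observed end score cannot be recovered. QIDS up to withdrawal and any mid-course HRSD-24 remain, so multiple imputation, a repeated-measures model, non-responder coding or bounds could keep everyone randomized. Excluding them is a choice made in section 7. These methods do rest on assumptions that cannot be tested.
- **Losses will fall more on one arm in a known direction.** Section 9.1 says blood-pressure falls are dose-dependent, but it describes their management without mentioning withdrawal, and section 6.3 does not define a serious reaction. Section 9.1 puts life-threatening complications below 1 in 10,000. If that is per anesthetic (an assumption), 30 × 10 = 300 Study 1 sessions give fewer than 300/10,000 = 0.03 expected. Selective loss is plausible; its direction and amount are unknown.
- **All new safety events are lost.** The exception can be read as covering a continuing AE, or any SAE, and section 6.3 requires reporting of all SAEs. New non-serious events are the part left uncovered.

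It is also fair to say that the wide bands need every lost participant in one arm to respond and none in the other, that treatment lasts only three weeks, and that continued assessment cannot prevent refusal. These points limit the size of the problem. They leave the rule and its effect on withdrawn participants in place.

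**Conclusion.** The point holds for participants withdrawn before treatment end: as written, the plan forbids collecting their final HRSD-24 and then excludes them. It also fails to distinguish stopping treatment from leaving the study, and it gives two triggers for the last rating. How many people this touches cannot be read from the documents.

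The 13, 40 and 67 point bands are extreme-case limits for assumed equal losses of 1, 3 and 5 per arm. They show sensitivity and do not predict bias. In the worked table, three losses per arm are enough for the result to turn on the missing-data assumption. The plan should be changed, since a score not taken at the time cannot be taken later and the remedy is cheap. The uncertain number affected and the remaining analysis options keep this short of a fatal flaw.

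**What to change.** Replace the last sentence of Subject Withdrawal and Study Completion with a rule of this kind: stopping study treatment for any reason, or withdrawal by an investigator, ends study treatment but not study assessments, unless the participant withdraws consent to them. Then:

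- Take the blinded HRSD-24, QIDS, MoCA, GAD-7 and WSAS at stopping, and again when the Post Tx visit would have been due, 48 to 72 hours after the scheduled date of treatment 10. Tying the visit to that date leaves completers' timing unchanged.
- Use one trigger for the final HRSD-24 in sections 5.3.1 and 6.3 and in the Schedule of Activities.
- Continue the monthly phone or REDCap follow-up, and record new non-serious AEs as well as continuing AEs and SAEs.
- Record any high-dose isoflurane or ECT received after deterioration, and state in section 7 how scores after such a switch are handled. Without this, a later HRSD-24 would partly measure the second treatment.

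No rule on when treatment stops is changed. The cost is protocol and consent wording plus a few extra contacts, some of which will be declined. The instruments and the remote route already exist in section 5.3.

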## **5. Clinical and Laboratory Evaluations**

### **5.1 Study Drug Administration and Duration**

All treatment groups, High ISO/BS+, Low ISO/BS- (Study 1) and propofol (Study 2) will receive 10 treatments over 3 weeks. All treatment procedures will take place in the ECT Procedure Room at the University of Utah Neuropsychiatric Institute. All participants will receive standard monitoring as recommended by the American Society of Anesthesiologists that includes EKG, pulse oximetry, blood pressure by noninvasive cuff, temperature, respiratory rate, and end-tidal carbon dioxide. If monitoring reveals significant hemodynamic alteration the anesthesiologist will manage the study participant by one or more of the following: IV fluid loading; Trendelenburg positioning; small bolus doses of ephedrine, phenylephrine, or epinephrine; or stopping the anesthesia. The course of action will be at the discretion of the anesthesiologist based on initial hemodynamics, absolute MAP change, and condition of the study participant. IV fluids will also be co-loaded at induction with the goal of replacing any deficit that resulted from fasting. The above noted anesthetic practices are routine and carried out on a daily basis in both the operating room and in the ECT suite.

**5.1.1 Study 1. High vs Low Dose Isoflurane (ISO):** The route and doses of isoflurane (both high and low doses) fall within the normal range of standard clinical practice. Details of induction follow, below:

Anesthetic Induction (High and Low Dose ISO): Anesthetic induction will be achieved with methohexital (1-3mg/kg IV). If there is a contraindication to methohexital, etomidate or propofol will be administered at the discretion of the anesthesiologist. General anesthesia will be administered via facemask. Patients will be co-loaded with IVF to offset any dehydration from fasting. Patients will be ventilated while under anesthesia using an LMA or ET tube as appropriate for safety and comfort.

High ISO/BS+ (n=15): The High ISO/BS+ group will receive isoflurane at the same level used in our previous study, with the initial vaporizer setting at 4%. End-tidal isoflurane concentration will be measured continually and is the best measure of alveolar concentration. Alveolar concentration will approximate effect site concentration. In this study we are directly measuring isoflurane effect on CNS electrical activity via the EEG (BIS) and burst suppression ratio is continually calculated and displayed. As the end tidal isoflurane concentration increases and the burst-suppression ratio increases, the vaporizer setting will be decreased. The goal is a burst-suppression ratio of 80%. Some burst suppression is seen at concentrations as low as 1MAC of isoflurane (1.15%) and most patients will achieve 80% BSR at 2 MAC or less (2.3%). These doses are well within the normal range for isoflurane use and are achieved on a daily basis in the O.R.s at this institution. As in the prior study by [name] et al , this condition of isoflurane-induced electrical quiescence will be maintained for 15 minutes.

Low ISO/BS- (n=15): ISO concentration will be titrated to maintain unconsciousness with burst suppression of  $\leq 20\%$ . This condition will be maintained for 15 minutes.

**5.1.2 Study 2. Open-Label Propofol Treatment:** Participants in the propofol treatment group will receive an induction dose of 2-3 mg/kg IV bolus, followed by propofol infusion at 100-400 mcg/kg/min. Additional boluses (0.5-2 mg/kg), administered every 2-3 minutes, may be necessary to achieve and maintain 80% burst suppression on EEG. At the end of the treatment, propofol administration will be discontinued and the participant will be allowed to awaken. Similar means of propofol induced burst-suppression is commonly and safely administered during neurosurgical procedures. Monitoring and supportive treatment will be consistent with clinical standards outlined by the American Society of Anesthesiologists as discussed above for participants in the main study. We will enroll up to 10 participants in the propofol pilot study.

**5.1.3 Anesthetic Emergence (All Treatments):** Emergence from isoflurane anesthesia into consciousness will be facilitated by the Aneclear device (QED 100™) according to FDA approved guidelines and as routinely used in the University of Utah operating rooms.

The time from discontinuing the intervention to when the participant responds to the repeated (every minute) command “Open your eyes” will be recorded. Participants will be monitored for AEs such as nausea, vomiting, and sore throat during anesthetic emergence. Orientation will be assessed repeatedly, beginning 3 minutes after eye opening, until the participant answers the questions correctly, e.g. “What day is it”, “Do you know where you are?” Perception of drug

effects during recovery will be assessed using the Drug Effects Questionnaire (DEQ). The total time for each session (estimated at 1.5 to 2.5 hours) will also be recorded.

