| QIDS, WSAS, Study XP  |           |          |        |   |   |   |        |   |   |        |   |    |         | X                                 |

 Study 1 only

 High ISO/BS+, Low ISO/BS-, or propofol

 Time to eye opening, time to sitting without dizziness, and time to ambulation and ingestion of liquids without vomiting. Occurrence rates of nausea and vomiting, presence of EKG abnormalities and somatic complaints, and total time for each will also be recorded. Orientation time will be assessed as the earliest time post-treatment at which a participant is able to recall 4 of 5 orientation items (name, date of birth, age, place, day of the week).

 An opened ended question about the participant's experience during the study

 Follow-up measures will take place monthly after the end of treatment series and will continue for 6 months.

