## **9. Protection of Human Subjects**

### **9.1 Potential Risks**

Isoflurane is a standard anesthesia induction agent. Its use has been shown to be effective in standard surgical care. Isoflurane is contraindicated if: 1) the participant is sensitive to isoflurane or other halogenated anesthetics, or 2) if the participant or a family member have had previous complications from anesthesia, specifically malignant hyperthermia.

Propofol is a well-tolerated, routinely administered anesthetic. Its use has been shown to be effective in standard surgical care. Propofol is contraindicated if the participant has an allergy to soy or peanuts.

The following risks are associated with anesthesia:

*Common (1-10%):* The participant may experience nausea, vomiting, and/or shivering from the anesthesia. Medications can be given to help with nausea and vomiting. These symptoms normally resolve within 60 minutes. Participants may also experience a mild sore throat from the breathing tube. For propofol group only: burning sensation at the injection site. After each anesthesia treatment, activities requiring mental alertness may be impaired for 2-4 hours. Therefore, we require participants to have someone accompany them home and recommend that they do not make any important decisions for 24 hours after treatment.

Both isoflurane and propofol anesthesia are associated with dose-dependent decreases in blood pressure. If monitoring reveals significant hemodynamic alteration, the anesthesiologist

will manage the study participant by one or more of the following: IV fluid loading; Trendelenburg positioning; small bolus doses of ephedrine, phenylephrine, or epinephrine; or stopping the anesthesia. The course of action will be at the discretion of the anesthesiologist based on initial hemodynamics, absolute MAP change, and condition of the study participant." IV fluids will also be co-loaded at induction with the goal of replacing any deficit that resulted from fasting. Blood pressure typically returns to normal after anesthesia is stopped.

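### Outside anaesthetic emergence, no scheduled question elicits adverse events other than mood, anxiety and cognition, and new non-serious events after withdrawal are not collected

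*Combined protocol and SAP*

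**What the plan says.** **Collection at emergence.** Section 5.1.3 states: "Participants will be monitored for AEs such as nausea, vomiting, and sore throat during anesthetic emergence". Footnote 3 of the Schedule of Activities, attached to the emergence row, adds: "Occurrence rates of nausea and vomiting, presence of EKG abnormalities and somatic complaints, and total time for each will also be recorded". Section 5.1.3 also uses the Drug Effects Questionnaire during recovery, and says of session length: "The total time for each session (estimated at 1.5 to 2.5 hours) will also be recorded".

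**Other safety measures.**
- Section 5.1: "All participants will receive standard monitoring as recommended by the American Society of Anesthesiologists".
- Section 5.3.2: the QIDS-SR is completed before each treatment, and "QIDS scores will also be used as a safety measure". MoCA, GAD-7 and WSAS are taken at baseline, before treatment 6 and 48-72 hours after treatment 10.
- Section 5.3.3 and schedule footnote 5: for 6 months, monthly contacts collect the QIDS-SR, the WSAS and one open question on the experience of taking part.
- Section 6.3: serious adverse events go to the DSMB and IRB within 5 days. Moderate events, among them worsening depression, go to the DSMB. Neither duty is limited to emergence.

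**Expected later effects.** Section 9.1: "After each anesthesia treatment, activities requiring mental alertness may be impaired for 2-4 hours".

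**Withdrawal.** Section 6.3: "If a participant has a serious reaction to anesthesia, they will be withdrawn from the study". Subject Withdrawal and Study Completion: "No information will be collected from withdrawn participants unless it is related to a continuing AE or SAE".

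**Use of the data.** Section 6.3 plans an interim analysis after 5 participants in each treatment condition, and ends the study if a treatment shows significantly more negative outcomes.

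**The concern.** An adverse event that nobody asks about is recorded only if the participant volunteers it or staff notice it. The plan prescribes adverse-event monitoring by name for one short period per session. The participant then goes home, and no later contact is scheduled to ask what happened in between. Somatic and other non-serious harms at home can go unrecorded.

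The withdrawal rule adds to this. It is an explicit instruction, not a gap to be filled by good practice. It applies to people who leave because of a serious reaction. It also applies to those who leave because their depression worsens, a case that section 9.1 foresees when it discusses treatment after leaving the study.

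Two uses of the data are at stake: the harm comparison in section 6.3, and the claim in the Background that this treatment may have a more favourable side-effect profile than ECT.

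**Working it through.** The plan gives no figure to reproduce here. The check sets its provisions side by side.

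**Step 1. Scheduled contacts that could ask about the preceding interval** (Schedule of Activities and footnotes 3-5; sections 5.3.2 and 5.3.3).
- Visits 2-10: 9 contacts. QIDS, monitoring, EEG, induction and emergence at each; HRSD, MoCA, WSAS and GAD-7 also before treatment 6. The emergence record concerns that day's anaesthetic, not the time since the last one.
- Post Tx: 1 contact. HRSD, MoCA, WSAS, GAD-7 and MRI/MRS.
- Monthly follow-up: 6 contacts. QIDS, WSAS and the open question.

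Total: 9 + 1 + 6 = 16 contacts. Number with a prescribed adverse-event question: 0 of 16. The open question at 6 of them might bring out an event, but its stated subject is the study experience.

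**Step 2. Expected effect against time in the clinic** (sections 9.1 and 5.1.3). Impairment is put at 2-4 hours after a treatment. The whole session, including induction and treatment, is put at 1.5-2.5 hours. Since 4 > 2.5, impairment at the upper end outlasts even the longest estimated session. At the lower end, 2 hours may or may not fit. The documents do not say how much of a session follows the anaesthetic, so the length of any unobserved period cannot be computed. The MoCA, taken before treatment 6 and 48-72 hours after treatment 10, is not timed to observe these hours.

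**Step 3. Two readings of the withdrawal rule.**

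| Event after withdrawal | If 'continuing' governs AE and SAE | If 'continuing' governs AE only |
|---|---|---|
| AE already under way | collected | collected |
| SAE already under way | collected | collected |
| New SAE | not collected | collected |
| New non-serious AE, including new worsening of depression | not collected | not collected |

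The last row is the same on both readings. Section 6.3 lists worsening depression among moderate events, so new worsening that is not serious falls in that row.

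**Step 4. What a withdrawal removes.** Take withdrawal after treatment 3 as an illustration. The scheduled contacts forgone are visits 4-10 (7), Post Tx (1) and six monthly contacts: 7 + 1 + 6 = 14. Of these, 7 + 6 = 13 carry a QIDS. For that person the plan's main mood safety measure stops too, unless the information relates to an event the rule still covers.

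**Step 5. Sensitivity of the section 6.3 look.** With 5 participants per condition, one participant whose event is unrecorded moves that group's observed proportion by 1/5 = 20 percentage points. At full enrolment the step is 1/15 = 6.7 points in an isoflurane arm and 1/10 = 10 points in the propofol group. This shows how much one missed participant weighs. It does not estimate how many are missed, or in which group.

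**The case against.** The strongest reply is that harm is looked for well beyond emergence. Physiological monitoring runs during every anaesthetic. The QIDS is a declared safety measure before every treatment. Anxiety and cognition are measured twice after baseline, and mood and function monthly for 6 months. Serious and moderate events are reportable whenever they occur. Footnote 3 follows participants until they walk and take liquids without vomiting. Section 9.1 says that nausea, vomiting and shivering normally resolve within 60 minutes, and it requires an escort home. The withdrawal rule keeps continuing events, which is what matters most for someone withdrawn because of a reaction.

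Most of this stands. A reader might infer that harms are sought only during emergence, or that all collection ends at withdrawal. The documents contradict both. For participants still in the study, mood, anxiety and cognition are measured outside emergence, and a reaction under way at withdrawal is followed.

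Three things remain. A reporting duty passes on events that staff already know about; it does not make anyone ask. The scales do not cover somatic or other non-serious harms at home. And new non-serious events after withdrawal are excluded on either reading of the rule.

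A reader might also infer that undercounting is greater in the deeper-anaesthesia groups, so that the termination rule leans towards a finding of safety. The documents do not support that. Section 9.1 states dose dependence only for blood pressure, and section 6.3 does not define negative outcomes, which could be depression scores rather than event counts.

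**Conclusion.** The point holds as a limited gap in ascertainment. Outside emergence, adverse events other than mood, anxiety and cognition are not systematically elicited: 0 of 16 later contacts carry such a question. After withdrawal, new non-serious events are not collected, and new serious ones are in doubt because the rule can be read two ways. The section 6.3 comparison may rest on incomplete counts. At 5 per condition each missed participant weighs 20 percentage points, but neither the number missed nor the direction of any bias can be derived.

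The conclusion assumes that the text not available for review, which appears to include section 8 (Training and Resources), contains no adverse-event procedure; the contents list shows no section for one. It also assumes that negative outcomes in section 6.3 include adverse events. If they mean depression scores alone, the missing general question matters less to that rule. The loss of QIDS data after withdrawal would still matter. Who enters the efficacy analysis is a separate question.

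**What to change.** 1. Add a row to the Schedule of Activities for a standard question on adverse events since the last contact, asked at the start of visits 2-10, at Post Tx and at the existing monthly contacts.
2. Amend Subject Withdrawal and Study Completion to separate stopping study treatment from withdrawing consent to data collection. Unless that consent is withdrawn, keep recording new adverse events, new serious adverse events and the QIDS through the existing phone or REDCap contacts to the end of the 6-month follow-up. This also removes the ambiguity about new serious events.
3. State in section 6.3 that its review includes these events.

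The cost is a few minutes per visit, some extra calls to participants who have stopped treatment, and changes to protocol and consent wording. No new visit is needed, and no dose or treatment rule changes.
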